### AF Subgroups

Subgroup analysis for subjects with AF and without AF will be presented. AF events adjudicated by the CEC will be used to identify subgroups.

- If a subject has at least one AF event as adjudicated by the CEC during the follow-up period, then the subject is in the "AF" subgroup
- If a subject does not have any AF events as adjudicated by the CEC during the follow-up period, then the subject is in the "No AF" subgroup

The number of events and the number of subjects in each subgroup will be reported overall and within each randomization arm. OAC medications may also be considered in the temporal pattern. A logistic regression model will be used to test the interaction between treatment and subgroup.

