# 6. Determination of Sample Size

### 6.1. Primary Objective

A total of 23 first events across the two treatment groups are required to demonstrate the primary objective of the study. Assuming 2% attrition from enrollment to randomization, approximately 486 subjects will be randomized. Subjects will be followed for 3 years, until end of device life or until official study closure, whichever occurs first. However, the primary objective of the study, upon which this sample size calculation is based, will be analyzed considering data up to the 12 months follow-up visit for all subjects in the study at the time of the analysis. This sample size calculation then assumes a follow-up time equal to 1 year and an accrual time equal to zero (data from all subjects is analyzed from randomization to the 12th month follow-up visit, regardless of how long they've been in the study at the time of the analysis). Withdrawn subjects will not be replaced.

The assumptions used for the calculations were:

- Two-sided log-rank test
- Alpha = 0.05
- 85% power
- Annual Attrition rate = 10% (in each treatment group)
- Annual Crossover rate = 5% (in each treatment group)
- Follow-up Time = 1 year
- Event-free one-year survival rate of 92% in the continuous monitoring arm
- Event-free one-year survival rate of 98% in the control arm (hazard ratio of 4.13)

This document is electronically controlled. Printed copies are considered uncontrolled.

Version 2.0 15/MAY/2017

The procedure "Logrank tests (Lakatos) using proportion surviving" in PASS 2008 was used to calculate the number of events required to test this objective.

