### 6.2. Secondary Objective

A number of 486 subjects randomized to achieve the primary objective and the assumptions below will also ensure 100% power to test the **secondary objective** of the study.

The assumptions used for the calculations were:

- Two-sided log-rank test
- Alpha = 0.05
- Annual Attrition rate = 10% (in each treatment group)
- Annual Crossover rate = 5% (in each treatment group)
- Accrual Time = 2 years
- Follow-up Time = 3 years
- Event-free survival rate of 80% in the continuous monitoring arm
- Event-free survival rate of 97% in the control arm (hazard ratio of 7.33)

The procedure "Logrank tests (Lakatos) using proportion surviving" in PASS 2008 was used to calculate the power to test this objective.

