### Recurrent Stroke Subgroups

Subgroup analysis for subjects with recurrent stroke and without recurrent stroke will be presented. Stroke events adjudicated by the CEC will be used to identify subgroups.

- If a subject has at least one stroke event as adjudicated by the CEC during the follow-up period, then the subject is in the "Stroke" subgroup
- If a subject does not have any stroke events as adjudicated by the CEC during the follow-up period, then the subject is in the "No Stroke" subgroup

The number of events and the number of subjects in each subgroup will be reported overall and within each randomization arm. A logistic regression model will be used to test the interaction between treatment and subgroup.

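### SAP 7.8 tests treatment-by-subgroup interaction in groups formed by AF or stroke after randomization; detected AF is the trial endpoint and is planned at 20% v 3% by arm, so the AF test does not estimate effect modification

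*SAP*

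**What the plan says.** SAP 7.8 defines three sets of subgroups. The first, by stroke subtype, uses the TOAST item on the baseline form and so is fixed before any monitoring effect.

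The other two are not. For AF the rule is "If a subject has at least one AF event as adjudicated by the CEC during the follow-up period"; everyone else is 'No AF'. For recurrent stroke it is "If a subject has at least one stroke event as adjudicated by the CEC during the follow-up period"; everyone else is 'No Stroke'. Both parts promise event and subject counts by arm and then carry the same sentence: "A logistic regression model will be used to test the interaction between treatment and subgroup". The AF part adds "OAC medications may also be considered in the temporal pattern". Neither part names the outcome of the logistic model.

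Adjudicated AF is also the endpoint of the primary and secondary objectives (SAP 7.9), and the sample size rests on a large difference between arms in detecting it. SAP 6.1 assumes "Event-free one-year survival rate of 92% in the continuous monitoring arm" against 98% in control. SAP 6.2 assumes "Event-free survival rate of 80% in the continuous monitoring arm" against 97% in control. Protocol 8.4.3.1 leaves rhythm monitoring of control subjects to each site's usual practice.

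**The concern.** An interaction test asks whether the effect of treatment differs between two kinds of patient. It can answer that only if the kind of patient is defined in the same way in both arms. Here the label depends on detection, and detection is what the intervention changes. A control subject with brief, silent AF is likely to be filed under 'No AF'; a similar subject with an ICM is likely to be filed under 'AF'. The interaction term then mixes unequal detection with any real effect modification. This holds for any outcome, because no choice of outcome turns a post-randomization grouping into a baseline one.

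At stake is interpretation. The p-value could be read as evidence about who benefits from monitoring, which it cannot show. Protocol 3.1 treats AF as a strong predictor of recurrent stroke, so moving AF patients between groups can matter for clinical outcomes.

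**Working it through.** **Inputs.** Randomized: about 486, 1:1, so 243 per arm (SAP 6.1, 5.3.1). AF by 12 months: 8% v 2% (SAP 6.1; protocol 12.1). AF over follow-up: 20% v 3% (SAP 6.2). Attrition 10% and crossover 5% per year in each arm (SAP 6.2).

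**1. The plan's own figures reproduce.** ln(0.92)/ln(0.98) = 4.13 and ln(0.80)/ln(0.97) = 7.33, the two stated hazard ratios.

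**2. Expected size of the 'AF' group.**

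| Basis | ICM | Control |
|---|---|---|
| 12 months | 243 × 0.08 = 19.4 | 243 × 0.02 = 4.9 |
| Whole follow-up | 243 × 0.20 = 48.6 | 243 × 0.03 = 7.3 |

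SAP 7.8 groups by the whole follow-up period, so the second row is the closer one.

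**3. With attrition.** Assume constant hazards and read 80% and 97% as 3-year rates. Then λ = −ln(0.80)/3 = 0.0744 (ICM) and −ln(0.97)/3 = 0.0102 (control), with attrition hazard δ = −ln(0.90) = 0.1054. The probability of detected AF is λ/(λ+δ) × [1 − exp(−3(λ+δ))].
- ICM: 0.1725 × 243 = 41.9.
- Control: 0.0257 × 243 = 6.3.

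Letting 5% per year move to the other arm's hazard as well gives 39.5 v 8.8.

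**4. How far the control 'No AF' group differs.** Assume that AF occurs equally in both arms and that AF found in control would also be found by an ICM. The share of control 'No AF' subjects who would have been 'AF' with an ICM is:
- 12 months: (0.08 − 0.02)/0.98 = 6.1%.
- Whole follow-up: (0.20 − 0.03)/0.97 = 17.5%, or about 41 of 236.
- With attrition: (41.9 − 6.3)/(243 − 6.3) = 15%.
- With attrition and crossover: (41.9 − 8.8)/(243 − 8.8) = 33/234 = 14%.

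The ICM arm is not free of this. Against complete 3-year ICM monitoring (48.6 found), attrition and crossover leave 48.6 − 39.5 = 9.1 of 203.5 ICM-arm 'No AF' subjects (4.5%) with AF not found. The like-for-like control figure is (48.6 − 8.8)/234.2 = 17.0%. The difference is one of degree, and it is large.

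**5. Can this alone produce an interaction?** Illustration only, with an assumed outcome and assumed risks. The outcome is recurrent stroke with no effect of monitoring. AF is present in 8% of both arms, stroke risk is 15% with AF and 5% without, the ICM finds all AF, and control finds it in 2% of subjects.
- Detection unrelated to stroke: control 'No AF' risk is (0.06 × 0.15 + 0.92 × 0.05)/0.98 = 5.6%, against 5.0% with ICM. The odds ratio in 'No AF' is 0.885 and in 'AF' 1.00, so the interaction odds ratio is 1.13.
- AF twice as likely to be found after a stroke: control 'AF' risk is 0.15 × 2/1.15 = 26.1%. The odds ratios become 0.50 ('AF') and 0.925 ('No AF'), so the interaction odds ratio is 0.54.

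A non-null interaction appears without effect modification, and its direction depends on inputs that the documents do not give.

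**The case against.** *The outcome and timing rules may sit in text we cannot see.* The ancillary-objectives row of the protocol synopsis has no content in the public copy, and the SAP's reference to a temporal pattern has no visible antecedent. This stands in part: such text might name the outcome or order AF and stroke in time. It could not make the grouping a baseline one.

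*The tests carry little weight.* This also stands. SAP 7.9 ties only the stroke-subtype subgroups to the two objectives, and no visible success criterion uses the AF or stroke tests.

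*The ICM arm also misses AF.* True. Protocol 8.4.2 and 8.4.6 keep subjects in the study without a device or after explant. A reader might infer that ICM 'No AF' subjects are truly AF-free; the plan's own attrition and crossover rates do not support that.

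*The stroke grouping is a weaker case.* Also fair: the documents give no recurrent-stroke rate by arm.

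A reader might go further and infer an inflated false-positive rate, a known direction of bias, or a control 'AF' group too small to fit the model. Each needs an outcome, a stroke risk and a link between detection and stroke that the documents do not supply. Protocol 8.4.5 requires an AF assessment after a recurrent stroke, so assuming that detection is unrelated to stroke is doubtful in any case.

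**Conclusion.** The point holds. The AF interaction test as written does not estimate effect modification, because its grouping variable is the trial's endpoint and is expected to differ by arm: about 49 v 7 subjects over follow-up (42 v 6 with attrition) and 19 v 5 at 12 months. About 17.5% of control 'No AF' subjects (15% with attrition) would have been 'AF' with an ICM. That share assumes equal AF occurrence in both arms and that an ICM finds whatever usual care finds; the attrition version adds constant hazards and 3-year rates. Undetected AF in the ICM arm is possible but expected to be less common.

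The stroke test shares the post-randomization grouping, but the size of any distortion cannot be stated. No false-rejection rate, direction of bias or empty-cell rate is claimed. A reader might infer that the trial's main results are compromised; they are not, since both log-rank tests compare the randomized arms without using these groups. Severity lies between minor and should-fix.

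**What to change.** In SAP 7.8:
- Delete the AF interaction test, and the recurrent-stroke one on the same principle.
- Keep the planned counts by arm, labelled as descriptive and as based on events after randomization.
- State that interaction is tested only in subgroups fixed at baseline, such as TOAST subtype.
- In any AF-stroke analysis that is kept, name the outcome and enter detected AF as a time-dependent variable, so that AF found after a stroke is not counted as preceding it. This is needed only if text not visible here does not already do so.

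The cost is SAP wording and two p-values. No new data are needed and no analysis of the primary or secondary objective changes.

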### Recurrent Stroke Subgroups

Subgroup analysis for subjects with recurrent stroke and without recurrent stroke will be presented. Stroke events adjudicated by the CEC will be used to identify subgroups.

- If a subject has at least one stroke event as adjudicated by the CEC during the follow-up period, then the subject is in the "Stroke" subgroup
- If a subject does not have any stroke events as adjudicated by the CEC during the follow-up period, then the subject is in the "No Stroke" subgroup

The number of events and the number of subjects in each subgroup will be reported overall and within each randomization arm. A logistic regression model will be used to test the interaction between treatment and subgroup.

### 7.9. Evaluation of Objectives

### **Primary Objective**

The primary objective is to compare the incidence rate of AF through 12 months between the continuous monitoring arm vs control arm in subjects with a recent ischemic stroke of presumed known origin.

This document is electronically controlled. Printed copies are considered uncontrolled.

Version 2.0 15/MAY/2017

### i. Hypothesis

 $H_0$ :  $h(t) = h_T(t)$  for  $t \le 12$  months

HA:  $h_c(t) \neq h_T(t)$  for  $t \le 12$  months

where  $h_T(t)$  and  $h_C(t)$  are the hazard functions of first detected and adjudicated AF at time t for subjects with and without the Reveal LINQ diagnostics for AF, respectively. Hazard functions and survival functions are transformations of each other.

### ii. Endpoint Definition

AF will be defined as an AF event lasting more than 30 seconds. The first AF episode detected and adjudicated by the endpoint adjudication committee will be used for this analysis.

### *iii. Performance Requirements*

The null hypothesis will be rejected if the two-sided log-rank test p-value is less than 0.05.

### iv. Analysis Methods

Arrhythmic episodes recorded by the subject's inserted/implanted device or from external monitoring will be adjudicated by the adjudication committee to determine if they meet the primary endpoint definition. Only first detected and adjudicated AF episodes within 12-months (365 days) will be included for analysis. Each subject's time to first detected and adjudicated AF will be defined as the time from randomization date to the date of first documented AF (i.e. the date of event per Reveal LINQ ICM, ECG, etc.) to meet the primary endpoint definition, and Kaplan-Meier curves will be generated for each randomization arm. Subjects who have not experienced an AF endpoint through 12 months will be censored at:

(1) their point of last contact, usable Reveal LINQ ICM interrogation or CareLink transmission if they occur before or at 12 months, whichever is later

or

(2) 12 months if their point of last contact, usable Reveal LINQ ICM interrogation or CareLink transmission go beyond 12 months.

A two-sided log-rank test will be performed to compare the rates between arms. The 12-month survival estimate with its 95% confidence interval will be reported for each arm. The hazard ratio estimate for the treatment effect with its 95% confidence interval will be reported.

The types of monitoring (i.e., wired monitor, wireless monitor, etc.) used to identify AF events in the control arm may be reported to further characterize the events.

This document is electronically controlled. Printed copies are considered uncontrolled.

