3.1. Background

Stroke is a devastating disease. In the United States (U.S.) more than 780,000 people experience a new or recurrent stroke each year; approximately 600,000 of these are first attacks and 180,000 are recurrent attacks. About 20% of patients die within the first year after having a stroke and another 20% are bound to a nursing home for the rest of their life. Furthermore, stroke is the fifth leading cause of death in the U.S. (when considered separately from other cardiovascular diseases) and the leading cause of serious long-term disability in the U.S. (Dariush Mozaffarian, 2015).

Of all strokes, 87% are ischemic (Dariush Mozaffarian, 2015), which occur as a result of decreased or insufficient blood flow to the brain. Patients with ischemic stroke (IS) are often treated with antithrombotic therapy. For most patients with IS, the mainstay of treatment is anti-platelet (AP) therapy with aspirin, clopidogrel, or aspirin+extended release dipyridamole. However, patients with IS who have been diagnosed with atrial fibrillation (AF) are normally treated with long-term oral anticoagulation (OAC), per recommendations within the AHA/ASA 2014 guidelines. OAC is dramatically more effective at preventing recurrent IS than AP therapy in patients with AF (Owen, 2009). In contrast, for patients without AF (or other rare cardiac sources of embolism), OAC has not been shown more effective than AP therapy. Therefore, detection of AF after IS is crucial, as it results in an important change in the administration of antithrombotic therapy from AP to OAC, thereby reducing the risk of recurrent stroke.

Episodes of AF are often asymptomatic, which makes detection of AF based on patient's symptoms unreliable (L. M. Christensen, 2014) (S. Adam Strickberger, 2005). Additionally, due to its episodic nature, AF is difficult to detect via intermittent monitoring techniques (Paul D. Ziegler, 2009). While AHA/ASA guidelines recommend cardiac monitoring of patients for up to 30 days after stroke, the optimum duration of monitoring is not known. It has generally been shown that longer durations of cardiac monitoring result in higher rates of AF detection after stroke. The advent of insertable cardiac monitors (ICM) allows continuous monitoring to detect infrequent episodes of AF for up to 3 years. Longer monitoring periods may be necessary to detect infrequent but clinically important paroxysms of AF (William C. Choe, 2015).

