Arrhythmic episodes recorded by the subject's inserted/implanted device or from external monitoring will be adjudicated by the adjudication committee to determine if they meet the primary endpoint definition. Only first detected and adjudicated AF episodes within 12-months (365 days) will be included for analysis. Each subject's time to first detected and adjudicated AF will be defined as the time from randomization date to the date of first documented AF (i.e. the date of event per Reveal LINQ ICM, ECG, etc) to meet the primary endpoint definition, and Kaplan-Meier curves will be generated for each randomization arm. Subjects who have not experienced an AF endpoint through 12 months will be censored at:

- their point of last contact, usable Reveal LINQ ICM interrogation or CareLink transmission if they occur before 12 months, whichever is later or
- 12 months if their point of last contact, usable Reveal LINQ ICM interrogation or CareLink transmission go beyond 12 months.

A two-sided log-rank test will be performed to compare the rates between arms.

In addition to the analysis on the full population, subgroup analysis for subjects with small vessel disease stroke and large vessel cervical or intracranial atherosclerosis stroke will be presented.

- vii. Determination of Patients/Data for Analysis
- All randomized subjects will be included in the analysis.

18 December 2018 Version 4.0 Page 52 of 66

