### 5.3. Treatment and Study Procedures

### 5.3.1. Treatment

Subjects are randomized 1:1 to the continuous monitoring arm or the control arm. Subjects randomized to the continuous monitoring arm will have a Reveal LINQ ICM inserted within 10 days of the qualifying stroke and undergo continuous remote monitoring. Subjects randomized to the control arm will be followed per site specific standard of care.

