### 056-F286, Statistical Analysis Plan Template, Version 2.0

### iv. Analysis Methods

Arrhythmic episodes recorded by the subject's inserted/implanted device or from external monitoring will be adjudicated by the adjudication committee to determine if they meet the secondary endpoint definition. Only first detected and adjudicated AF episodes during all follow-up will be included for analysis. Each subject's time to first detected and adjudicated AF will be defined as the time from randomization date to the date of first documented AF (i.e. the date of event per Reveal LINQ ICM, ECG, etc.) to meet the secondary objective endpoint definition.

Each subject's time to first detected and adjudicated AF will be defined as the time from randomization date to the date of first documented AF (i.e. the date of event per Reveal LINQ ICM, ECG, etc.) as in the secondary endpoint definition above, and Kaplan-Meier curves will be generated for each randomization arm. Subjects who have not experienced an AF endpoint through the duration of the study follow-up will be censored at their point of last contact, usable Reveal LINQ ICM interrogation or CareLink transmission, whichever is later.

A two-sided log-rank test will be performed to compare the rates between arms. Survival estimates with 95% confidence intervals will be reported for each arm. The hazard ratio estimate for the treatment effect with its 95% confidence interval will be reported.

The types of monitoring (i.e., wired monitor, wireless monitor, etc.) used to identify AF events in the control arm may be reported to further characterize the events.

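### Kaplan-Meier with deaths implicitly censored overstates the proportion of patients with detected AF: negligible at 12 months, modest but growing by 3 years; report cumulative incidence as well

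*SAP*

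**What the plan says.** For the primary objective, Protocol 12.1 states that "Kaplan-Meier curves will be generated for each randomization arm", and SAP 7.9 (Primary Objective, iv. Analysis Methods) adds that "The 12-month survival estimate with its 95% confidence interval will be reported for each arm". For the secondary objective, over all follow-up, SAP 7.9 says "Survival estimates with 95% confidence intervals will be reported for each arm" and names no time point.

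In both analyses a subject without AF is censored at the latest of last contact or last usable device data, capped at 12 months for the primary. Death has no rule of its own. SAP 7.4 says only that time-to-event methods leave data missing solely for subjects with no follow-up. Neither document mentions competing risks or a cumulative incidence function.

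The objectives are worded as AF incidence. The protocol treats incidence as one minus event-free survival: the rationale in 12.1 expects 8% and 2% at 12 months, and the sample size assumptions enter these as 92% and 98% event-free.

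**The concern.** A patient who dies without AF can no longer have AF detected. Censoring that patient assumes that the later AF risk would have matched that of the survivors, so one minus Kaplan-Meier answers a hypothetical question: how much AF would be found if nobody died. The proportion of randomized patients in whom AF is found is smaller. The gap widens with follow-up and, when death rates are similar in the two arms, is larger in absolute terms where AF detection is higher. The difference between arms is then overstated too.

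That difference is the absolute yield of monitoring. Protocol 3.2 and 5.3 present the trial as support for bringing the monitor into the care pathway and as evidence that could influence guidelines, and absolute yield matters for both. The longer-term figure, from the secondary objective, is the more exposed.

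**Working it through.** **Inputs from the documents.** SAP 6.1: event-free at one year 92% (monitoring) and 98% (control), annual attrition 10% and annual crossover 5% in each group, "approximately 486 subjects will be randomized", and "A total of 23 first events across the two treatment groups are required to demonstrate the primary objective of the study". SAP 5.3.1: 1:1 allocation, so 243 per arm. SAP 6.2: event-free 80% and 97% with 3 years of follow-up. These last two are read here as 3-year figures, which the SAP does not state outright.

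**Plan's own figures first.** ln(0.92)/ln(0.98) = 4.127 (stated 4.13), and ln(0.80)/ln(0.97) = 7.326 (stated 7.33). Expected events before any loss are 243 × (0.08 + 0.02) = 24.3. A Lakatos-type calculation with 486 subjects, one year, 10% loss and 5% crossover in each arm gives 23.1, in line with the stated 23.

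**Assumption.** The documents give no death rate for this trial. Annual death probability m is set at 3%, 5% and 10%, constant and equal in both arms. The 10% case requires all planned attrition to be death.

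**Formulas.** With constant hazards, λ = −ln(S)/T for AF and μ = −ln(1 − m) for death.
- One minus Kaplan-Meier: 1 − exp(−λT) = 1 − S.
- Cumulative incidence: λ/(λ + μ) × [1 − exp(−(λ + μ)T)].

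Example, monitoring arm, 3 years, m = 10%: λ = 0.22314/3 = 0.07438 and μ = 0.10536. Then 0.07438/0.17974 = 0.4138, and 1 − 0.80 × 0.90³ = 0.4168. The product is 0.1725, against 0.20 by Kaplan-Meier.

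| | 1 − KM | m = 3% | m = 5% | m = 10% |
|---|---|---|---|---|
| Monitoring, 12 months | 8.0% | 7.88% | 7.80% | 7.60% |
| Control, 12 months | 2.0% | 1.97% | 1.95% | 1.90% |
| Monitoring, 3 years | 20.0% | 19.15% | 18.59% | 17.25% |
| Control, 3 years | 3.0% | 2.87% | 2.78% | 2.57% |
| Arm difference, 12 months (points) | 6.0 | 5.91 | 5.85 | 5.70 |
| Arm difference, 3 years (points) | 17.0 | 16.3 | 15.8 | 14.7 |

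Simulation of the 3-year monitoring arm gave 18.58% at m = 5% and 17.26% at m = 10%, matching the formula.

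**Scale.** The 95% half-width per arm with 243 subjects and no loss is 1.96 × √(0.08 × 0.92/243) = 3.4 points at 12 months and 1.96 × √(0.20 × 0.80/243) = 5.0 points at 3 years. The monitoring-arm excess is 0.1 to 0.4 points at 12 months and 0.9 to 2.8 points at 3 years. Relative to the cumulative incidence, the 3-year excess is 4.5% (0.85/19.15) to 16% (2.75/17.25).

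**The case against.** **Only a descriptive estimate is at issue.** The hypotheses are stated as hazard functions and success is the log-rank p-value. This stands. With deaths censored, the log-rank test and hazard ratio compare cause-specific hazards and remain valid. A reader might infer that the primary result is at risk; it is not.

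**The size is within sampling error.** This stands for annual deaths of 3% to 10%: negligible at 12 months, and inside the half-width at 3 years. But the error always runs in the same direction, and the confidence interval is built around the same shifted quantity, so it does not correct for it.

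**The death rate may be low.** A reader might take the background statement in Protocol 3.1, "About 20% of patients die within the first year after having a stroke", and conclude that the distortion is clear-cut. The documents do not support that. The figure is for stroke patients generally, whereas this trial excludes subjects with life expectancy under one year. It covers the first year only, and it is twice the planned 10% attrition from all causes. Sustained for three years it would give 14.8% instead of 20%. With 20% in the first year and 5% a year after, the figure is 16.2%. Even 10% a year leaves no room for withdrawal or loss to follow-up, both of which Protocol 8.4.7 lists as exit reasons.

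**The survival estimate is a legitimate quantity, and extra analyses are allowed.** The SAP does call its output a survival estimate, and SAP 3 and 7.12 permit additions. But the objectives speak of incidence, the protocol equates incidence with one minus that estimate, and nothing commits the sponsor to the alternative.

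**An opposite bias exists.** Censoring at the later of last contact or device data can count unmonitored time as AF-free, which lowers detected incidence. This is a separate problem, and the net direction of the two together is not established here.

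**Conclusion.** The point holds in a limited form. Censoring of deaths is implied, not written, and under it one minus Kaplan-Meier overstates the proportion of patients with detected AF by an amount that grows with follow-up. At 12 months this has no practical consequence. At 3 years the overstatement is modest: for assumed annual deaths of 3% to 10%, the arm difference of 17.0 points shrinks by 0.7 to 2.3 points.

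These sizes rest on constant hazards, equal death rates in both arms, the planning event-free rates, and other losses being unrelated to AF risk. If most attrition is withdrawal or loss to follow-up, the low end applies. To call the 3-year overstatement clear or large would need a death rate that the documents do not give. The log-rank test, hazard ratio, 23 events, sample size and primary conclusion stand. This is a cheap improvement, not a flaw in the trial's main inference.

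**What to change.** In SAP 7.9, mainly under the secondary objective and for the final report:

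- State that subjects who die without AF are censored in the log-rank and Cox analyses.
- Report Aalen-Johansen cumulative incidence of first adjudicated AF per arm with 95% confidence intervals, treating death before AF as a competing event, at 36 months and, for consistency, at 12 months.
- Keep the Kaplan-Meier curves and estimates as supplementary.

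The cost is a few lines of SAP text and one extra analysis. Date of death is already collected (Protocol 10.3.1.1). The SAP was written from version 2 of the protocol, now at version 4.0, so the change can go in with any realignment. The downside is a slightly lower reported incidence. The change does not address unmonitored time being counted as AF-free, which needs its own treatment.
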